## Background

Extensive peritoneal disease or peritoneal carcinomatosis represents an aggressive mode of spread for many tumors which ultimately results in death. In most cases progression of the intraperitoneal disease precedes distant metastasis and patients typically die of complications related to the intraperitoneal disease. There is no standard chemotherapy which has shown promise in the treatment of peritoneal carcinomatosis for adults or children. The extent of retroperitoneal disease can limit complete surgical resection and the intensive post-operative chemotherapy regimens are only useful if a complete response (CR) is evident. For sarcomatosis as is found in desmoplastic small round cell tumor (DSRCT), if residual disease is present there have been no survivors after intensive chemotherapy even with stem cell rescue. (1) This may be related to the difficulty in obtaining cytotoxic concentrations of chemotherapy within the tumor parenchyma. A regional approach to treating the intraperitoneal tumor is appealing as a means of delivering high concentrations of chemotherapeutic agents directly to the tumor while limiting systemic toxicity. (By means of using the peritoneal surface as barrier to systemic absorption) (2) This approach has been demonstrated to be very effective for advanced ovarian cancer, appendiceal carcinoma and has become the standard care for adults in many cancer centers. (3) In phase I and II clinical trials, this strategy has also been found to improve disease free survival in mesothelioma and gastric cancer. (4-6)

DSRCT primarily presents in children and young adults age 5-30, 90% male, with dozens to hundreds of abdominal tumor implants. Less than 200 cases are reported in the world literature and therefore treatment options are limited. Despite chemotherapy, aggressive tumor debulking and radiotherapy, 3 year survival is 20-30%. After aggressive tumor debulking of Desmoplastic round cell tumor (DSRCT), various strategies have been employed which direct therapy toward the peritoneal disease because of the characteristic loco-regional pattern of spread. Such approaches have included intraoperative radiation therapy (IORT) and hyperfractionated radiation therapy. (7-10) Some chemotherapy and radiation responses have been documented, but local abdominal recurrence shortly follows. While these approaches attest to the acknowledged importance of controlling intra-abdominal disease, they have not been uniformly successful in the long term complications of secondary tumors. (11-13)

Other rare pediatric tumors which can recur and metastasize in the abdominal cavity include Wilms' tumor, colon carcinoma, sarcoma, and malignant ovarian germ cell tumor. With advanced intraperitoneal disease, these tumors are usually fatal despite aggressive chemotherapy and radiation therapy. In a novel approach to these aggressive tumors, here at UT MDACC, an investigator initiated phase I study found that continuous hyperthermic peritoneal perfusion, also known as HIPEC, is safe in children.

HIPEC is a technique for combining hyperthermia and chemotherapeutic agents delivered intraoperatively to the peritoneal and retroperitoneal surface via a recirculating perfusion circuit. (14) In addition to adult clinical trials, the support for this concept comes from in vivo and in vitro laboratory studies. The selective lethal effect of supranormal temperatures on human and murine neoplastic cells has been well established in laboratory models. (15-17) A variety of cell lines including colon carcinoma and melanoma have been shown to be sensitive to temperatures ranging from 42 to 45°C when exposed for a period of 2 to 4 hours while their non-neoplastic parental cell types are largely unaffected. In vivo, there appears to be a differential

response of normal and tumor microcirculation in response to hyperthermia. (18) In response to hyperthermia, normal tissue will show a dramatic and temperature dependent increase in blood flow at temperatures up to 50°C. In contrast, blood flow through neoplastic tissue will increase to a much smaller extent and stasis occurs at lower temperatures which are well tolerated by normal tissue. Therefore, there appears to be two fundamental mechanisms by which supranormal temperatures can be selectively toxic to neoplastic cells via both direct cytotoxic effects and vascular stasis.

As mentioned, for drugs administered into the peritoneal cavity, the simultaneous systemic administration of neutralizing agents can provide protection against the systemic toxic effects of drug which leaks into the circulation. Systemic sodium thiosulfate has been shown to covalently bind and inactivate cisplatin in the systemic circulation and obviate the expected renal toxicities. The use of sodium thiosulfate allows the administration of high doses of intraperitoneal cisplatin which might result in blood levels comparable to an intravenous administration of drug. (19) A loading dose of sodium thiosulfate, followed by continuous infusion has completely prevented any substantial rise in serum creatinine with doses of cisplatin up to 270 mg/M administered intraperitoneally with a 4-hour dwell time.

The major disadvantage of intraperitoneal drug administration appears to be that drug uptake by tumor tissue is mostly through capillary diffusion rather than capillary flow. With cisplatin in a normothermic environment, tumor penetration up to 3 mm has been shown. This would theoretically be adequate to penetrate a tumor deposit 6 mm in diameter. Thus it is clear that aggressive surgical debulking, leaving minimal gross residual disease, will be optimal for the maximum therapeutic effect with cisplatin.

In adult studies of carcinomatosis, there were no procedure related mortalities; morbidity included renal impairment, ascites, and pancreatitis. Dose limiting toxicity included grade III leukopenia, grade IV neutropenia and grade III and IV thrombocytopenia at the higher doses only (greater than 800 mg/M). (20, 21) Specifically, no patient had a prolonged postoperative ileus and no adverse effect on wound healing was observed. Following surgery, the median time before tolerating enteral feeds was 5 days (range 1-7 days), and patients could tolerate a regular diet at a median of 7 days (range 4-8 days). Neither patient who had undergone bowel resection and anastomosis followed by HIPEC had any anastomotic complication. One patient suffered a subfascial hematoma incurred from trauma to the left inferior epigastric artery. (20) In the mesothelioma study, the MTD of cisplatin was 300 mg/M. Above this dose there were significant rises in creatinine and one patient required temporary hemodialysis. (21) There have not been any untoward effects of the HIPEC on the ability of these patients to heal incisional wounds and convalesce uneventfully.

This intraoperative treatment using HIPEC in children has provided some very encouraging results. The phase I study of HIPEC in children done here (protocol #2005-0917) proved to be safe. There were no protocol related deaths. Two SAE's included temporary cardiomyopathy likely related to the 4 kg+ tumor resected and supraventricular tachycardia likely related to central venous catheter malposition. Several children had temporary increased creatinine, up to 1.9. However, no problems were seen with urinary output; serum creatinine returned to normal within 1-2 weeks without treatment or dialysis.

Preliminary results suggest 3 year disease free survival is 71% (compared to 26% in historic controls) and disease free interval is increased 5 times from 1.6 to 9 months in the subset of patients with DSRCT. The 2 sarcoma patients died within 6 months and one mesothelioma patient is alive with minimal disease. Another mesothelioma patient in 3rd relapse was treated with surgery + HIPEC is >2 years from surgery. In summary there appears to be benefit in many and we have reached a dose limiting toxicity (DLT), elevated creatinine using HIPEC with cisplatin at 150 mg/M.

### Rationale

Desmoplastic small round cell tumor (DSRCT) is a rare disease of children, adolescents and young adults, which begins in the abdominal cavity. Less than 200 cases are reported in the world literature. The primary organ of DSRCT origin is the peritoneum. It is a very unique tumor that is difficult to treat because of the infiltrative and diffuse nature of the peritoneum. Patients may present with dozens to hundreds of tumors studding the peritoneal cavity. DSRCT was only recently described in 1991 and since then multimodality treatment including chemotherapy, radiation and aggressive surgery, has not improved outcome. Here at UT MDACC the PI has conducted a phase I trial in children with 'carcinomatosis' who underwent continuous hyperthermic peritoneal perfusion using cisplatin after cytoreductive surgery. (This was an investigator initiated trial and we were the only center in the North America embarking on this effort)

For continuity, we propose to open the phase II study on the subset of patients with the best prognosis after HIPEC, those with DSRCT. In data not yet published, we compared the 9 patients with DSRCT who have undergone HIPEC with 15 historical adolescent and adult patients with DSRCT at UT MDACC who had chemotherapy +/- radiation therapy only and no HIPEC and found a survival advantage of 41 weeks in the patients undergoing HIPEC, a 3 year median survival of 26% for those not undergoing HIPEC and 71% for those who had HIPEC. This is very preliminary data with few patients and follow up is only 1-3 years. Further study of HIPEC in DSRCT is warranted. The surgical study plan and delivery of hyperthermic chemotherapy are the same as the previously approved phase I protocol. The maximum tolerated dose, the safe dose of cisplatin found in phase I, is 100 mg/M. Pediatric and adult patients with other non-carcinoma tumors with extensive peritoneal disease will be eligible if no standard HIPEC treatment has been established for these patients. Results of the research analysis will not be shared with the patient during the conduct of this study nor will the results influence the clinical strategy.

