### 1.0 Primary objectives of the study

**Primary objective 1:** To determine the efficacy of HIPEC using hyperthermic cisplatin given as a continuous perfusion after complete abdominal tumor excision in patients with DSRCT.

**Primary objective 2:** To determine the morbidity of extensive tumor resection and HIPEC on patients with DSRCT and other non-carcinoma tumors with extensive abdominal disease.

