## 4.2 Response Criteria and Statistical Considerations

4.2.1 This is a phase II study of continuous hyperthermia peritoneal perfusion (HIPEC) in patients with desmoplastic round cell tumor (DSRCT) and non-DSRCT patients. The primary objective is to assess the efficacy of this treatment, with a primary endpoint of time to relapse. The historical median time to relapse for DSRCT patients without HIPEC treatment was about 1.6 months. A maximum of 22 patients will be enrolled in MDACC at an estimated accrual rate of 1 patient every 2 months including a total of 5 non-DSRCT patients. Patients will be followed up until relapse, death or for 6 months after the treatment, whichever ever occur first. It would be encouraging if the median time to relapse could increase to 3.2 months with the HIPEC treatment. The toxicity and efficacy will be monitored during the study, and all the data will be used to update the prior distributions for toxicity and efficacy parameters. The study will be stopped for toxicity and futility based on the following stopping rules.

4.2.2 The primary endpoint TTP will be monitored using the method of Thall et al. (23). Denote median (TTP) =  $m_H$  for patients without HIPEC treatment and  $m_E$  for patients with HIPEC treatment. We assume that TTP is distributed exponentially with mean of  $m_H$  and  $m_E$ , respectively, in patients without and with HIPEC treatment. Under a Bayesian model, we will further assume that  $m_H$  has an inverse gamma (IG) prior with parameters (16.2, 24.3), with a mean of median TTP=1.6 months and variance = 0.18. We also assume that  $m_E$  follows IG prior (2.03, 1.64) with the same median TTP as  $m_H$  but with a much larger variance (100) to reflect much greater uncertainty about TTP in patients with HIPEC treatment. The TTP data will be monitored continuously, and the study will be terminated early if  $\Pr(m_H + d < m_E \mid \text{data}) < 0.05$ , where  $d = 1.6$  month. Specifically, the trial will be stopped early if, given the current data, there is less than 5% chance that the median TTP will improve by more than 1.6 month in patients treated with HIPEC, compared to those without HIPEC treatment. The operating characteristics of this decision rule are summarized in [Table 1](#).

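### The 1.6-month benchmark appears to come from patients not described as debulked, so a favourable result would reflect surgery, selection and HIPEC together, not HIPEC alone

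*Combined protocol and SAP*

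**What the plan says.** Primary objective 1 (section 1.0) is "To determine the efficacy of HIPEC using hyperthermic cisplatin given as a continuous perfusion after complete abdominal tumor excision" in patients with DSRCT. Objective 2, on morbidity, names tumor resection and HIPEC together.

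There is no concurrent control. Section 4.2.1 sets the comparator: "The historical median time to relapse for DSRCT patients without HIPEC treatment was about 1.6 months". It adds: "It would be encouraging if the median time to relapse could increase to 3.2 months with the HIPEC treatment". Section 4.2.2 gives the benchmark median m_H an inverse gamma "prior with parameters (16.2, 24.3), with a mean of median TTP=1.6 months and variance = 0.18". The trial stops early if Pr(m_H + 1.6 < m_E | data) falls below 0.05.

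The only DSRCT comparison group the protocol describes is in the Rationale: "15 historical adolescent and adult patients with DSRCT at UT MDACC who had chemotherapy +/- radiation therapy only and no HIPEC". The outcome reported there is "a 3 year median survival of 26% for those not undergoing HIPEC and 71% for those who had HIPEC". The Background gives the same 26% and 71%, this time labelled disease free survival, and the same sentence says that "disease free interval is increased 5 times from 1.6 to 9 months in the subset of patients with DSRCT".

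Trial patients differ from that description. Sections 2.1.3 and 2.1.4 require disease confined to the abdomen that can be debulked to deposits of 1 cm or less. Under 3.1.2 surgery comes first, and under 3.1.2 and 4.8.4 patients who cannot be debulked are not perfused and leave the study. Section 4.6.1 permits any post-operative chemotherapy. The analysis plan in 4.2.4 has no adjustment or sensitivity analysis for differences from the historical group.

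**The concern.** A single-arm trial can attribute to its experimental component only what the benchmark leaves out. If the benchmark patients were not debulked and were not selected for being debulkable, m_E minus m_H contains the effect of cytoreduction, the better prognosis of resectable abdominal disease, and any difference in when the clock starts, as well as any effect of HIPEC.

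The protocol's own reasoning makes surgery more than a neutral background factor. The Background reports no survivors in DSRCT when residual disease remained after intensive chemotherapy, and calls aggressive debulking optimal for the effect of cisplatin.

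At stake is what the trial may conclude. A median time to relapse well above 1.6 months would be read, under objective 1, as efficacy of HIPEC. The design cannot distinguish that from efficacy of the operation in selected patients.

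**Working it through.** **1. Where the 1.6 months comes from.** No sentence says it was measured in the 15 patients. Three things point that way:
- The Rationale ties 26% versus 71% to the 15 patients. The Background gives the same pair in the sentence that contains the 1.6 months.
- Both the Rationale group and the 4.2.1 benchmark are described as patients without HIPEC.
- The prior carries about the information that 15 patients would give. For an inverse gamma (a, b), mean = b/(a − 1) = 24.3/15.2 = 1.599 and variance = mean²/(a − 2) = 1.599²/14.2 = 0.180. Both match the plan. The information is 1.6²/0.18 = 14.2, or about 14 events.

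**2. What the contrast contains.**

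| | Described historical group | Trial patients |
|---|---|---|
| Surgery | not mentioned; described as having chemotherapy with or without radiation only | all debulked before perfusion |
| Selection | DSRCT, adolescent and adult | abdomen-confined and debulkable; others removed at surgery |
| Time origin | not stated | treatment (follow-up runs to 6 months after it) |
| HIPEC | no | yes |

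HIPEC is one of several rows that differ.

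**3. Exposure from the plan's own Table 1.** Early stopping is 0.775 at a true median of 1.6 months and 0.178 at 3.2 months. The rule sees only the median, not its cause. If surgery and selection alone gave 3.2 months, the trial would escape the futility stop with probability 1 − 0.178 = 0.822, against 1 − 0.775 = 0.225 at 1.6 months.

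**4. Exposure at intermediate values.** Settings: 17 DSRCT patients (22 maximum less 5 non-DSRCT), one patient every 2 months, exponential time to relapse, censoring at 6 months, a look before each enrolment, priors IG(16.2, 24.3) and IG(2.03, 1.64), and 20,000 trials per row. The parameter is read as the median both in generating and in updating. HIPEC is set to add nothing. The multipliers are assumed, since the documents give no surgery-alone time to relapse.

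| Assumed multiplier | True median (months) | Pr(stop for futility) |
|---|---|---|
| 1 | 1.6 | 0.95 |
| 1.25 | 2.0 | 0.83 |
| 1.5 | 2.4 | 0.69 |
| 2 | 3.2 | 0.46 |

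These do not reproduce Table 1 (0.95 against 0.775 at 1.6 months; 0.46 against 0.178 at 3.2 months). Section 4.2.2 calls m both the median and the mean of the exponential, which is a separate matter. Both sets of figures move the same way: the more surgery and selection contribute, the less often an inert HIPEC is stopped.

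**The case against.** **The protocol does not say the controls had no surgery.** That reading rests on the word *only* in a one-sentence summary of unpublished data. The terms disease free interval and time to relapse suggest that at least some of these patients were rendered disease-free. This stands. A reader might infer that the benchmark is known to come from unoperated patients with a different time origin. The documents support only that surgical history and time origin are unstated.

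**Surgery may add little.** The Rationale says multimodality treatment including aggressive surgery has not improved outcome. The Background gives 20-30% three-year survival despite debulking, and the controls' 26% lies inside that range. This stands as evidence that the surgical contribution to survival may be small. It does not give time to relapse after surgery in patients selected as debulkable, so it does not remove the confounding.

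**The benchmark is not treated as nearly known.** A reader might infer that from the variance of 0.18. In fact the prior has an SD of 0.42 and a 95% interval of 0.97 to 2.61 months, with about 15% probability above 2.0. Its width suits a sample of about 15. But that width expresses sampling error in the historical group, not a difference between the two populations.

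**The rule is for futility only.** Passing it is not a declaration of efficacy, 3.2 months is called only encouraging, and the protocol describes a phase II pilot with its surgical component disclosed. That is fair, and a single-arm design is reasonable in a disease with fewer than 200 reported cases. Objective 1 nevertheless assigns efficacy to HIPEC, and no other comparison is planned that could support it.

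**Steeper figures should not be used.** Generating data with 1.6 as the median while updating as if it were the mean gives stop probabilities from about 0.74 down to about 0.27. Reading the parameter consistently as the mean gives about 0.96 down to 0.47, close to the table above. The lower series reflects the mean/median mismatch, not historical-control bias.

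**Conclusion.** The concern holds in limited form. As designed, m_E versus m_H measures cytoreductive surgery, patient selection and HIPEC together, and a favourable result cannot be credited to HIPEC alone as objective 1 does. This rests on two inferences, both reasonable and neither stated: that the 1.6 months belongs to the 15 patients, and that their description means they were not, as a group, debulked.

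The size of the bias is unknown and could be small. The figures of 82% from Table 1 and 0.95 falling to 0.46 from simulation show how exposed the rule is under assumed surgery/selection effects. They do not estimate the effect of surgery. The trial can run as planned; what needs correcting is the claim and the reporting around it.

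**What to change.** 1. Word objective 1 and the efficacy conclusion as *cytoreductive surgery plus HIPEC*, in line with objective 2, and state that the design does not isolate HIPEC. State also the surgical history and time origin of the group that gave the 1.6 months.

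2. Add to 4.2.4 a sensitivity analysis of the final posterior Pr(m_H + 1.6 < m_E | data) with m_H multiplied by 1.25, 1.5 and 2 (assumed values) and d kept at 1.6 months. Scaling m_H multiplies only the second prior parameter:
   - × 1.25: IG(16.2, 30.375), mean 30.375/15.2 = 2.0 months
   - × 1.5: IG(16.2, 36.45), mean 36.45/15.2 = 2.4 months
   - × 2: IG(16.2, 48.6), mean 48.6/15.2 = 3.2 months

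3. If existing records contain DSRCT patients debulked without HIPEC, report their time to relapse from surgery as an additional benchmark. The documents do not show that such patients exist, so items 1 and 2 should not wait for this.

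The cost is a narrower claim, a few posterior calculations and, for item 3, a chart review. Treatment, visits and sample size do not change.

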### 1.0 Primary objectives of the study

**Primary objective 1:** To determine the efficacy of HIPEC using hyperthermic cisplatin given as a continuous perfusion after complete abdominal tumor excision in patients with DSRCT.

**Primary objective 2:** To determine the morbidity of extensive tumor resection and HIPEC on patients with DSRCT and other non-carcinoma tumors with extensive abdominal disease.

## **Methods and Research Plan**

The current study is designed to evaluate the efficacy of HIPEC with cisplatin, in children adolescents and young adults with disseminated intra-peritoneal disease. This phase II pilot study will include aggressive surgical debulking, in patients with abdominal desmoplastic small round cell tumor.

### 2.0 ELIGIBILITY ASSESSMENT AND ENROLLMENT

#### 2.1 Inclusion Criteria

- 2.1.1 Age greater than or equal to 1 year.
- 2.1.2 Histologically or genetically proven diffuse peritoneal or retroperitoneal tumor from desmoplastic round cell tumor, ovarian germ cell, sarcoma, Wilms' tumor, or other non-carcinoma tumors.
- 2.1.3 Radiologic workup must demonstrate that the disease is confined to the abdominal cavity
- 2.1.4 Radiologic workup or prior abdominal exploration must be consistent with disease which can be debulked to a residual size of less than or equal to 1 cm thickness per tumor deposit
- 2.1.5 Patients must have a minimum expected duration of survival of greater than 6 weeks as determined and documented by the attending surgeon or medical oncologist.
- 2.1.6 Patients must not have any systemic illness which precludes them from being an operative candidate as determined by anesthesia preoperative evaluation. This includes but is not limited to, sepsis, liver failure, pregnant or lactating females.
- 2.1.7 Patients must have fully intact mental status and normal neurologic abilities. Intact mental status is defined by 'the capacity to identify and recall one's identity and place in time and space.' Assessment of mental status and documentation of fully intact mental status will be completed using physical and mental exam by the referring doctor or oncologist.
- 2.1.8 Patients must have adequate renal function (serum creatinine  $\leq$  1.5 mg/dl without history dialysis or renal failure or creatinine clearance less than 50 mL/min/1.73 M if less than 5 years of age)
- 2.1.9 Patients will be eligible if the WBC is  $\geq$ 2000/ $\mu$ l or ANC is  $\geq$ 1,500 and platelets are  $\geq$  100,000/mm^3
- 2.1.10 Patients will be eligible if serum total bilirubin and liver enzymes are  $\leq$  2 times the upper limit of normal
- 2.1.11 Patients must be recovered from any toxicity from all prior chemotherapy, immunotherapy, or radiotherapy and be at least 14 days past the date of their last treatment

